9.7.4 Analysis Cohort

The intent-to-treat cohort (ITT) will be defined as those who were randomized. It will be used for analyses of baseline characteristics, protocol deviations and violations, and trial conduct. The evaluable cohort (Eval) is a subset of ITT participants. Evaluable participants will be defined as participants who complete the Screening and Enrollment visits and return for their day 7 visit within the window for a safety assessment. Non-evaluable participants will be replaced.

TABLE 5: Statistical Analysis Plan

Endpoint	Variable	Statistics
Primary	Adverse Events	Frequency, Percent
	MK-2048 concentration	Mean, SD, Median, Range,
Secondary	Acceptability	Frequency, Percent

Exploratory	Persistence of Eudragit® in CVL defined as any concentration above the lower limit of quantification	Mean, SD, Median, Range
	Levels of glycoproteins and mucins, in CVL	Mean, SD, Median, Range
	Antiviral activity in CVL	Mean, SD, Median, Range
	Change in vaginal flora (Nugent score)	Frequency, Percent, Median, Range
	Culture/qPCR results from vaginal organisms - prevalence	Frequency, Percent
	Culture/qPCR results from vaginal organisms - concentration	Mean, SD, Median, Range
	Change in cytokine and innate immunity factors	Mean, SD, Median, Range
	HIV infection of cervical biopsies in ex vivo challenge	Mean, SD, Median, Range

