7.4 Visit 3, 4, 5, 6, 7 and 8: Follow-Up Visits

Visit 3, 4, 5, 6, 7 and 8 procedures are outlined in Table 4. The windows around these study visits are as follows:

Visit 3: Day 3 (2-4)

Visit 4: Day 5 (5-6)

Visit 5: Day 7 (7-8)

Visit 6: Day 10 (9-12)

Visit 7: Day 14 (13-16)

Visit 8: Day 28 (24-32)

Two cervical biopsies will be obtained at Visit 5 only. A CVL will be performed at Visits 7 and 8. Residual drug, if present, will be removed during the CVL at Visit 7. The purpose of Visit 8 is to provide a final safety assessment.

Table 3: Follow-up Visit Procedures

VISIT 3, 4, 5, 6, 7, 8 FOLLOW-UP VISITS	
Component	Procedure/Analysis
ADMINISTRATIVE	
 • Collect/Update Contact Information • Visit Questionnaire • Update medical history and concomitant medications • Protocol counseling excluding Visit 8 (including effective birth control, sexual practices restrictions and vaginal product use) • Assess/Document Adverse Events • Schedule Next Study Visit (excluding Visit 8) • Participant Reimbursement
ACCEPTABILITY	
 • Acceptability Questionnaire (Visit 5 ONLY; prior to biopsy)
BLOOD	
 • MK-2048 level
URINE	
 • Pregnancy test (Visit 5 & 8 and as clinically indicated) • Urine dipstick, as clinically indicated
VAGINAL	
 • pH • Wet Mount, prn • Trichomonas (NAAT), as clinically indicated • Gram Stain • Quantitative Vaginal Culture • Quantitative PCR for microbiota • Vaginal swab for MK-2048 level • Vaginal sample for Future Use*
RECTAL	
 • Rectal swab for MK 2048 (Visit 5 ONLY)
CERVICAL	
 • GC/CT (NAAT), as clinically indicated • Cervical biopsies- two adequate (Visit 5 ONLY) • Cervical sample for Future Use*
CVL (Visits 7 and 8 only)	
 • Levels of antiviral activity • • Levels of glycoproteins and mucins • Levels of cytokines & innate immunity factors • MK-2048 level • Eudragit® levels
PHYSICAL EXAM	
 • Physical Exam, as clinically indicated • Vital Signs (BP)

PELVIC EXAM	
 • Bimanual Exam, as clinically indicated • External Genital & Speculum Exam
--------------------	--

* For participants who have consented to the collection of samples for future use and use of left-over samples for future studies.

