8.3 Adverse Events Definitions

An AE is defined as any untoward medical occurrence in a clinical research participant administered an investigational product and which does not necessarily have a causal relationship with the investigational product. As such, an AE can be an unfavorable or unintended sign (including an abnormal laboratory finding, for example), symptom or disease temporally associated with the use of an investigational product, whether or not considered related to the product. This definition is applied to all groups beginning from the time of randomization.

Study participants will be provided instructions for contacting the study site to report any untoward medical occurrences they may experience, except for possible life-threatening events, for which they will be instructed to seek immediate emergency care. Where feasible and medically appropriate, participants will be encouraged to seek evaluation at UPMC Magee-Womens Hospital, where the study clinicians are based, and to request that a study clinician be contacted upon their arrival. All participants reporting a clinically significant untoward medical occurrence will be followed either in person or by phone until the occurrence resolves (returns to baseline) or stabilizes over a four week period.

Study site staff will document AEs reported by or observed in enrolled study participants regardless of severity and presumed relationship to study product.

For each study participant, AE documentation and reporting will be undertaken throughout the scheduled duration of follow-up, i.e., through Visit 8.

The PI/designee will grade the severity of each AE and the relationship of the AE to study product:

AE severity will be graded per the DAIDS Table for Grading Adult and Pediatric Adverse Events, Version 2.1, July 2017 and the Female Genital Grading Table for Use in Microbicide Studies (Appendix 1, version 1.0, November 2007) except that asymptomatic BV will not be considered an AE. AEs not included in the Female Genital Grading Table will be graded by the DAIDS AE Grading Table Version 2.1, July 2017. In cases where a genital AE is covered in both tables, the Female Genital Grading Table for Use in Microbicide Studies will be the grading scale utilized.

The relationship of all reported AEs will be assessed based on the Manual for Expedited Reporting of Adverse Events to DAIDS (Version 2.0, dated January 2010) and the clinical judgment of the PI/designee.

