8.5 Clinical Management of Adverse Events

By definition, an adverse event can be either new finding or symptom or a worsening of a pre-existing condition. In order to accurately capture adverse events in follow-up, a thorough baseline history will be obtained at Visit 1 and Visit 2. For example, for participants who endorse a history of headache, site staff will probe for and record details surrounding the condition such as frequency, location, duration, medication use, triggers, etc. Only by eliciting a full description will study staff be equipped to determine whether a subsequent event in follow-up is a clinically distinct event or not.

Adverse events will be elicited at each follow-up visit. Referral to appropriate care will be offered to participants as needed. The study site is well equipped to manage treatment of all sexually transmitted infections and vaginitis identified during screening or during study participation except for HIV. Participants who are found to be HIV infected will be referred for care. The PI/designee should manage STI/RTI per CDC guidelines, available at <http://www.cdc.gov>. Observed single dose treatment should be provided whenever possible. Vaginally applied medications should not be used if possible.

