8.7 Criteria for Early Termination of Study Participation

Participants may voluntarily withdraw from the study for any reason at any time. The Site PI/designee also may withdraw participants from the study to protect their safety and/or if they are unwilling or unable to comply with required study procedures. Participants also may be withdrawn if the study sponsors, government or regulatory authorities, including the Office of Human Research Protections (OHRP), or site IRBs/ECs terminate the study prior to its planned end date. Every reasonable effort is made to complete a final evaluation of participants who withdraw or are withdrawn from the study prior to completing follow-up. Study staff members will record the reason(s) for all withdrawals in participants' study records.

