9.2 Sample Size and Accrual

The primary aim of the study is to assess the local and systemic safety of a single dose of two formulations of an MK-2048 vaginal film. The primary endpoint is the proportion of participants who experience a Grade 2 or higher adverse event. The proposed total sample size is N=48 divided into 2 arms (low and high Eudragit® content assigned at a 1:1 ratio). Based on previous studies of vaginal products conducted at the study site, the accrual of 48 eligible subjects with normal reproductive tracts is expected to require the screening of approximately 90 volunteers. Since unevaluable participants will be replaced, it is anticipated that 48 women exposed to study product will be evaluable for the primary endpoint.

The sample size is based on the exact binomial probability of observing Grade 2 or higher adverse events. **Table 4** gives the upper and lower bounds for the 95% exact binomial confidence intervals of the true Grade 2 or higher adverse event rate at all possible numbers of observed events in a group of size 24 or in the full cohort of 48. Note that the results for more than 50% of events in each group are not listed, but by symmetry can be calculated as 1- the listed rate and 95% CI for the number of non-events. If none of the 48 subjects experience Grade 2 or higher adverse events, the 95% exact 2-sided upper confidence bound for the Grade 2 adverse event rate is 7.4%. In a previous study of a single dose of the high Eudragit® content placebo film, 6 grade 2 adverse events were reported in a cohort of 64 women for an event rate of 9.4%. If similar event rates are observed in the proposed study, we will be able to rule out grade 2 or higher adverse event rates greater than 22.6% in the full cohort and 32.4% in each study arm.

TABLE 4: 95% confidence intervals for the true rate at all possible observed Grade 2 or higher adverse event rates

Number of observed events	Rate (95% CI)	Number of observed events	Rate (95% CI)
0/24	0 (0, 14.2%)	0/48	0 (0, 7.4%)
1/24	4.2% (0.1%, 21.1%)	1/48	2.1% (0%, 11.1%)
2/24	8.3% (1.0%, 27.0%)	2/48	4.2% (0.5%, 14.3%)
3/24	12.5% (2.7%, 32.4%)	3/48	6.2% (1.3%, 17.2%)
4/24	16.7% (4.7%, 37.4%)	4/48	8.3% (2.3%, 20.0%)
5/24	20.8% (7.1%, 42.2%)	5/48	10.4% (3.4%, 22.6%)

6/24	25.0% (9.8%, 46.7%)	6/48	12.5% (4.7%, 25.2%)
7/24	29.2% (12.6%, 51.1%)	7/48	14.6% (6.1%, 27.8%)
8/24	33.3% (15.6%, 55.3%)	8/48	16.7% (7.5%, 30.2%)
9/24	37.5% (18.8%, 59.4%)	9/48	18.8% (8.9%, 32.6%)

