9.7.2 Primary Endpoint Analysis

The number of adverse events will be summarized by severity, body system, and relationship to study product using frequencies and percent. Individual participants will contribute once to the calculation of event rates. Differences in the prevalence of adverse events between the study arms will be assessed using Fisher's exact test.

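### The primary Grade 2+ adverse event rate appears to cover only women who return on days 7–8, so a recorded event in a dosed woman who does not return then drops out of the rate

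*Combined protocol and SAP*

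**What the plan says.** Section 9.7.4 defines two cohorts. The intent-to-treat cohort is everyone randomized, and its uses are listed: "It will be used for analyses of baseline characteristics, protocol deviations and violations, and trial conduct". Safety is not among them. The second cohort is the evaluable one: "Evaluable participants will be defined as participants who complete the Screening and Enrollment visits and return for their day 7 visit within the window". The stated purpose of that day 7 visit is a safety assessment, and women who do not qualify are replaced. Section 7.4 sets the window at days 7–8.

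Section 9.2 carries evaluability into the primary endpoint: "Since unevaluable participants will be replaced, it is anticipated that 48 women exposed to study product will be evaluable for the primary endpoint". Table 4 then uses 48, or 24 per arm, as the denominators.

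Section 9.7.2 describes the primary analysis without naming a cohort; it says only "Individual participants will contribute once to the calculation of event rates". Table 5 names none either.

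Collection of adverse events is wider than evaluability. Section 8.3 applies the definition from randomization and adds "For each study participant, AE documentation and reporting will be undertaken throughout the scheduled duration of follow-up, i.e., through Visit 8". Section 8.5 says "Adverse events will be elicited at each follow-up visit", which takes in Visits 3 and 4 (days 2–6), before the evaluability visit.

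**The concern.** Attendance on days 7–8 happens after exposure. A safety rate restricted to women who attend is conditioned on something the product can influence. If women with events are less likely to return in the window, the rate and its upper bound are too low, which is the wrong direction for safety. If non-return has nothing to do with events there is no systematic bias, but observed events are still thrown away.

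The documents foresee ways to be dosed and then become non-evaluable. Section 8.7 allows voluntary withdrawal and adds "The Site PI/designee also may withdraw participants from the study to protect their safety". Section 10.3 provides for visits outside the window. Section 5.3 itself names bias from loss to follow-up as something to minimize.

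Safety is the only primary objective, section 10.2.1 describes this as the first human use of these films, and the study is sized on the exact confidence interval. That interval is the main quantity at risk; the Fisher comparison is a lesser one. Monthly review and the enrolment pause in section 8.2 still see every event, so participant oversight is not affected. The reported primary result is.

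**Working it through.** **Which women are in the rate**

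1. Two cohorts exist (9.7.4). The listed uses of the intent-to-treat cohort leave out safety.
2. The other cohort is defined by an in-window safety visit, and section 9.2 describes its 48 women as evaluable for the primary endpoint.
3. The primary analysis text (9.7.2) does not override this, and no section returns a replaced woman's event to the rate.
4. Late attendance shows the effect. A woman who misses days 7–8 and is next seen on day 9 is inside the Visit 6 window (days 9–12, section 7.4). Her adverse events are assessed, yet she is non-evaluable and is replaced.

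**Reproducing the plan's figures**

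Inputs: two-sided 95% exact binomial limits, 48 women, 24 per arm (9.2). For x events in n women:

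- lower = Beta quantile 0.025 with parameters (x, n − x + 1)
- upper = Beta quantile 0.975 with parameters (x + 1, n − x)
- for x = 0, upper = 1 − 0.025^(1/n)

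Results: 0/48 gives 1 − 0.025^(1/48) = 7.40%; 5/48 gives 22.66% (the plan prints 22.6%); 3/24 gives 32.36%. All rows of Table 4 agree within 0.1 point.

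**Effect of one excluded woman who had a Grade 2+ event**

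The documents give no loss rate, so the number excluded is an assumption. Each excluded dosed woman adds 1 to the denominator, and 1 to the numerator if she had an event.

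| Evaluable only | Upper bound | All dosed | Upper bound | Change in bound (points) |
|---|---|---|---|---|
| 0/48 = 0% | 7.40% | 1/49 = 2.0% | 10.85% | 3.5 |
| 5/48 = 10.4% | 22.66% | 6/49 = 12.2% | 24.77% | 2.1 |
| 3/24 = 12.5% (one arm) | 32.36% | 4/25 = 16.0% | 36.08% | 3.7 |

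**Range under other assumptions, starting from 5/48 (upper bound 22.7%)**

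| Replaced women (assumed) | All-dosed rate | Upper bound |
|---|---|---|
| One, lost event-free, counted as a non-event | 5/49 = 10.2% | 22.2% |
| One, lost event-free, counted as an event | 6/49 = 12.2% | 24.8% |
| Three: one with an event, two lost event-free counted as non-events | 6/51 = 11.8% | 23.9% |
| Three: as above, the two counted as events | 8/51 = 15.7% | 28.6% |
| Six, none with an event | 5/54 = 9.3% | 20.3% |
| Six, all with an event | 11/54 = 20.4% | 33.5% |

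Six is the ceiling because the randomization list has 54 places (9.6): 54 − 48 = 6. Section 9.6 also reserves those places for unusable product, so six replaced dosed women is an extreme.

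**Fisher test**

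At planning-level counts, 2/24 against 3/24 gives p = 1.00. Restoring one event to the first arm, 3/25 against 3/24 also gives p = 1.00.

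**The case against.** The strongest reply is that the exclusion is inferred. No sentence assigns the primary analysis to the evaluable cohort. Section 9.7.4 gives that cohort no explicit analytic use, and the wording in 9.2 sits in a sample size section, where it may only explain why 48 is the planning number. Replacement can mean enrolling another woman without deleting data. An all-dosed adverse event table is therefore not expressly ruled out. This stands as a limit on certainty. It does not remove the problem: if the primary safety population has to be inferred, and the available text points to evaluable women, the plan needs correcting on either reading.

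The second reply is that loss driven by adverse events is unlikely. The film is a single clinician-placed dose, so there is no continuing treatment to stop. Section 8.3 follows clinically significant events in person or by phone, section 7.6 allows interim visits for events, and section 8.7 seeks a final evaluation of women who leave. Sections 5.3 and 10.3 support retention and reward in-window attendance. All of this should keep exclusions few, but none of it changes who is counted.

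The third reply is that the effect is small and assumed, and that no decision threshold is tied to the upper bound. That is fair. An event-free excluded woman would even lower the all-dosed bound slightly (22.7% to 22.2%), and the Fisher result does not move.

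Finally, section 2.3 cites earlier human trials of vaginal MK-2048 and of the film polymer, so first human use applies to these films and not to their components.

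**Conclusion.** The concern holds and should be fixed. On the natural reading of sections 9.2 and 9.7.4, a dosed woman with a recorded Grade 2+ event who does not attend on days 7–8 is replaced and leaves the primary rate. Confidence in that reading is moderate, because no sentence states it.

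If one such woman exists, the reported upper bound is about 2 to 4 percentage points too low. With no events among evaluable women, the plan could report 0/48 when an event is on file. These sizes rest on assumed exclusions; the documents allow neither the number nor the direction of any bias to be derived. A low bias requires non-return to be related to adverse events.

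**What to change.** In sections 9.7.2 and 9.7.4:

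- Define the primary safety set as all randomized women in whom a film was inserted, analysed by film received.
- Count every Grade 2+ event from randomization through Visit 8 or last contact, whether or not Visit 5 was attended or in window.
- Report the exact 95% intervals per arm and pooled, and run the Fisher test, on that set.
- Add replacements to the denominator instead of substituting them, and state that the 48 and 24 in Table 4 are minimum denominators.
- Keep the evaluable cohort as a sensitivity analysis for safety.
- List replaced women by arm with reason, adverse events and length of follow-up.
- Give a bounding analysis that counts women lost event-free before day 7 first as non-events and then as events, since counting them only as non-events can pull the rate down.

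The first four items remove the defect; the last three show how much it matters. The cost is a paragraph of analysis wording, one listing and one small table, with no new data, visits or participants. The reported rate may be slightly less favourable. If an all-dosed analysis was always intended, naming that set needs only one clarifying sentence.

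### Women qualify for the primary Grade 2+ proportion at Day 7, but adverse events run to Visit 8 (Day 28); as written, event-free women lost in between would count as non-events

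*Combined protocol and SAP*

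**What the plan says.** Section 9.2 defines the endpoint: "The primary endpoint is the proportion of participants who experience a Grade 2 or higher adverse event". It sizes the trial on exact binomial intervals with denominators of 24 per arm and 48 in total, and explains how those will be reached: "Since unevaluable participants will be replaced, it is anticipated that 48 women exposed to study product will be evaluable for the primary endpoint".

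Section 9.7.4 defines evaluable women as "participants who complete the Screening and Enrollment visits and return for their day 7 visit within the window for a safety assessment" and adds: "Non-evaluable participants will be replaced". Nothing after Day 7 is required.

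Section 8.3 sets a longer period for the events themselves: "AE documentation and reporting will be undertaken throughout the scheduled duration of follow-up, i.e., through Visit 8". Section 7.4 places Visit 5 at Day 7 (window 7-8) and Visit 8 at Day 28 (window 24-32), and describes Visit 8 as the final safety assessment.

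On analysis, section 9.7.2 says "Individual participants will contribute once to the calculation of event rates" and compares arms with Fisher's exact test. Table 5 lists frequency and percent for adverse events. Neither section contains a censoring, person-time, missing-outcome or sensitivity rule for the primary endpoint.

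**The concern.** The visit that admits a woman to the denominator comes about one quarter of the way through the period in which her events count. A two-cell analysis has no place for a woman who was event-free when last seen on, say, Day 8. She is evaluable, so she is not replaced, and with no recorded Grade 2+ event she falls in the non-event cell. The resulting rate describes events while observed, for at least 7 days, rather than events through Visit 8.

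The unobserved period is not obviously free of risk:

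- Two cervical biopsies are taken at Visit 5 itself (section 7.4), and section 10.2.1 lists bleeding over the following days and infection among their risks.
- In FAME-101 the placebo film was still visible in 25% of women assigned to Day 14 follow-up (section 2.2).
- Section 7.4 has residual drug removed only at Visit 7.
- Section 8.7 allows withdrawal to protect a woman's safety, so loss could be related to risk.

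The error can only lower the apparent rate and its upper bound, which is the figure the trial was sized on. If losses differ between films, it would also distort the comparison between arms.

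**Working it through.** **1. The plan's own figures.** Two-sided 95% Clopper-Pearson upper bounds:

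| Observed | Rate | Recomputed upper bound | Section 9.2 |
|---|---|---|---|
| 0/48 | 0% | 7.4% | 7.4% |
| 5/48 | 10.4% | 22.7% | 22.6% |
| 3/24 | 12.5% | 32.4% | 32.4% |

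The 5/48 difference is in the last digit only (22.66% unrounded). The plan's figures reproduce. They treat every woman's outcome as known.

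**2. Share of the window after the evaluability visit.** (28 - 7)/28 = 21/28 = 75%.

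**3. Expected bias if losses stay in as non-events.** Let R be the true risk through Visit 8, f the share of first events occurring after Day 7, and L the share of women still event-free who are lost just after Day 7, with loss unrelated to risk. Then

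expected crude rate = R(1 - f) + R·f·(1 - L), so bias = -R·f·L.

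R = 9.4% is the section 9.2 reference rate (6/64). The documents give neither f nor L, so the ranges below are assumptions.

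| f | L = 5% | L = 10% | L = 20% |
|---|---|---|---|
| 0.25 | -0.1 | -0.2 | -0.5 |
| 0.50 | -0.2 | -0.5 | -0.9 |
| 0.75 | -0.4 | -0.7 | -1.4 |

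Entries are percentage points. For example, 9.4 × 0.75 × 0.20 = 1.41. With L = 0 the bias is zero.

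**4. What the upper bound could hide.** Take 5 observed events in 48, with m event-free women lost after Day 7.

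| m | As planned | Followed to Visit 8, or with an event | All lost counted as events |
|---|---|---|---|
| 0 | 5/48, upper 22.6% | 5/48, upper 22.6% | 5/48, upper 22.6% |
| 2 | 5/48, upper 22.6% | 5/46 = 10.9%, upper 23.6% | 7/48 = 14.6%, upper 27.8% |
| 5 | 5/48, upper 22.6% | 5/43 = 11.6%, upper 25.1% | 10/48 = 20.8%, upper 35.0% |

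The planned figure does not change with m. The bounds for 5, 7 and 10 of 48 are rows of Table 4.

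**5. Per arm.** From Table 4, 3/24 has upper bound 32.4%. One lost woman counted as an event gives 4/24 (37.4%); two give 5/24 (42.2%).

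**6. Zero events.** The planned bound is 7.4% at 0/48 whatever the loss. With five women lost, the bound on the 43 followed to Visit 8 is 8.2%; in the worst case it is the 5/48 bound, 22.6%.

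**The case against.** The strongest reply is that the documents nowhere say these women are counted as event-free. Section 9.7.2 says only that each woman contributes once. Section 9.7.4 assigns uses to the intent-to-treat cohort but never names the analyses that use the evaluable cohort. The endpoint definition in section 9.3.1 carries no time window. All of this is true, and a reader who infers a written rule that losses are non-events, or a rate that is certainly biased, goes further than the text. What stands is narrower. Section 9.2 does link evaluability to the primary endpoint, section 8.3 does set the collection period, and a percentage with Fisher's test leaves an evaluable woman with no recorded event only the non-event cell.

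A reader might also take the randomization list of 54 (section 9.6), 6 above the planned 48, as an expected loss of 6/54 = 11.1% and build a larger bias on it. The documents do not support that. The overage covers withdrawals and unusable product. Replacement applies to non-evaluable women, whereas a woman lost after Day 7 is evaluable. It says nothing about loss after Day 7.

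The plan also works to limit loss: retention steps and immediate follow-up of missed visits (section 5.3), a final evaluation attempted at withdrawal (section 8.7), a wide Visit 8 window, and an incentive for completing all visits in window (section 10.3). A woman who misses Visit 6 or 7 but attends Visit 8 loses little information. These measures may make L small, but they do not say how remaining losses are counted.

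Finally, the expected bias is small against a 5/48 interval running from 3.4% to 22.6%, about 19 points wide, and the worst case requires every lost woman to have had an event. Both points stand. They argue for a short clarification with a sensitivity line rather than a change of design.

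**Conclusion.** The mismatch is real: evaluability is settled at Day 7, events count through Visit 8, and the planned analysis does not separate women followed for 7 days from those followed for 28. If any event-free evaluable woman is lost after Day 7, the rate through Visit 8 and its upper bound are understated.

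The expected size is modest, about 0.1 to 1.4 points at a 9.4% rate. That rests on assumed losses of 5-20% just after Day 7, 25-75% of first events falling later, and loss unrelated to risk. Loss concentrated in higher-risk women would make it larger; full follow-up makes it zero. The upper bound is more fragile, because in 48 women two losses are enough to leave anything up to 27.8% open where the plan would report 22.6%. The conclusion is conditional on losses occurring and does not show that the reported rate will be wrong. It is still worth settling before the data are seen, because safety is the sole primary objective and the bound is the basis for the sample size.

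**What to change.** In sections 9.7.2 and 9.7.4:

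1. State that the primary risk window is randomization through Visit 8, and that an event-free woman who leaves before Visit 8 is not counted as a full non-event.
2. Keep the planned crude proportion with its exact interval, and report two results beside it, per arm and pooled:
   - **Day 28 risk** as 1 minus Kaplan-Meier, censoring at the last adverse event assessment, with a 95% interval. With zero events the usual interval collapses, so give the exact binomial bound on women followed to Visit 8 instead.
   - **Worst case**, counting event-free losses after Day 7 as events, with the Clopper-Pearson interval and Fisher's test repeated.

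Kaplan-Meier assumes that loss is unrelated to risk, so it does not remove bias from risk-related withdrawal; the worst-case line covers that. With complete follow-up both estimates equal the planned proportion.

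The cost is a few lines of text and minor programming, with no added women or visits. The downside is a slightly less favourable reported rate and upper bound if women are lost.
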